# **SECTION II: GENERAL INFORMATION**

1. Choose all that apply: (* See indicated s	section in HIC Guidelines for Investigators)
Children/minors* (Section E.1)	Pregnant women/fetuses/placenta
Decisionally impaired* (Section E.2)	) Prisoners
Females of childbearing potential	Non-English Speaking
Radioactive Materials	Use of Employees
☐ IND #	Students
Page 1	of 28

#### APPROVED BY THE YALE UNIVERSITY IRB 6/15/2023

Principal Investigator: [name]

MAY 2023 HIC #0407026910

	IDE #	A or B (Section C.1)		
2.	billable to the subject, the Yes No [	sponsor or other third party payer?	ervices to human subjects that may be ister this study in the IDX/GE system NewStudyRequest.pdf	
3.	 	se identify the hospital, in-patient of the location of the research.	r outpatient facility, school or other	
	APT Foundation, Inc.	Connecticut Mental Health Cente	er Department of Veterans Affairs,	
We	est Haven			
	Haskins Laboratories	☐ John B. Pierce Laboratory, Inc	Magnetic Resonance Research	
Ce	nter (MR-TAC)			
	PET Center	☐ Yale Cancer Center	☐ Yale New Haven Hospital HRU	
	YCCI/Church Street Research	arch Unit (CSRU)	XCCI/Hospital Research Unit	
YCCI/Keck Laboratories				
[name]				
	Please indicate the location	n(s) within the hospital and/or Medica	al School where the research will take	
	place:			
Scanning will take place at the Anlyan Building MRI Center, Interviewing at the Yale University				
	School of Medicine, and t	he blood draw at the YCCI/Hospital	Research Unit (HRU).	
		_		

Please note: when other institutions are engaged in the research, it may be necessary to secure the approval of their Institutional Review Boards (IRB) and/or to insure that the institution has obtained a Federal Wide Assurance (FWA). Institutions may not list the Yale HIC as their IRB of record unless the Federal government has approved their FWA and they have in place a fully executed IRB Authorization Agreement between their institution and Yale University.

- 4. **Probable Duration of Project**: Please state the expected duration of the project, including all follow-up and data analysis activities. Sample collection will take place over a period of at least 20 years 7 months and probably considerably longer. DNA will be retained indefinitely.
- **5. Number of Subjects:** Please state the number of subjects to be enrolled at Yale. For multi-center studies, indicate the total number of subjects to be enrolled across all sites. If different subject populations will participate, state the anticipated number in each group. The total is 1029:

396 participants with mood disorders, 50 participants with an attention deficit disorder and 300 healthy comparison participants are anticipated to be enrolled overall. Exclusion criteria are more stringent for the imaging component and thus only a subset will be eligible for the imaging component.

Also, a subgroup of 100 adolescents, ages 13-17 years, will be recruited from a well-characterized cohort from a longitudinal study conducted by [name] HIC #5149 "The Long Term Impact of Intrauterine Cocaine Exposure" (also known as "The Infant and Young Children's Follow-Up Project").

In addition, a subgroup of 12 subjects who do not meet criteria for bipolar disorder, but who are "at-risk" for bipolar disorder (as they have at least one first degree relative with bipolar disorder) although they do not meet criteria for having the disorder.

Also, 20 subjects (comprised of both healthy control subjects and subjects diagnosed with mood disorders) for a pilot study utilizing the 7T scanner. In addition, for the R21, 26 subjects with bipolar disorder and 26 healthy comparison subjects, ages 16-23 years, to undergo the 7T imaging. There will be no increase to the target enrollment with the addition of the psychotherapy pilot study. Subjects already participating in the imaging component of the study are invited to participate in a pilot treatment study, with initial aim of 10 pilot subjects.

For a combined psychotherapy (BE-SMART) and imaging study, 66 subjects who meet criteria for BDI, BDII, BD-OS for an R61 grant, and 20 additional subjects in the R61 Supplement, ages 16-29 years, who will receive, along with the psychotherapy, the wireless actigraphy device (e.g. GENActiv) that is worn on the wrist and monitors a person's activity when in motion or at rest/sleep and Ecological Momentary Assessment (EMA) electronic diary in which subjects enter their ratings into a handheld electronic device each day on their emotions, behavior, and activities.

In addition, 13 "at risk" subjects for bipolar, ages 13-21 years with DSM-5 diagnosis of MDD and a parent with BDI or BDII. These subjects will not be randomized but will participate in the down regulation BE-SMART therapy for the KGTF grant.

#### SECTION III: RESEARCH PLAN

1. **Statement of Purpose:** What are the scientific aims of the study, or the hypotheses to be tested? **Purpose of the Genetic Component (formerly HIC Protocol 22336):** The purpose of this protocol is to collect blood or saliva for genetic and biochemical (to include neurotrophic and immune factors recently associated with mood disorders) analysis from individuals with mood disorders or an attention deficit disorder and healthy controls in order to look at associations between regional brain abnormalities and specific genotypes and biomarkers that may be associated with mood disorders or attention deficit disorder. The long term scientific goal of the project is to identify genetic loci, and alleles at those loci, that influence vulnerability to mood disorders, attention deficit disorder and related phenotypes, such as prefrontal dysfunction. In addition, study across the lifespan will help to contribute to our understanding of the interaction of genetic vulnerabilities with abnormalities in brain development associated with the onset of the disorders. Prior to 5/11/2023, a sample from this study may have been obtained and submitted to a data repository run by the National Institute of Health. Samples/data from subjects newly enrolled after 5/11/2023 were no longer shared and will continue not to be shared unless NIH funding becomes available. Only data/specimens collected during the NIH funding period will be shared with NIH.

# Purpose of the Imaging, and Integrated Imaging and Genetic Components (contains components of former HIC Protocol 11005):

## **Primary Aims:**

**Aim #1:** Use a prospective longitudinal design and structural MRI to examine age-related changes in amygdala (AMYG) and orbitofrontal cortex (OFC) volumes and to examine ventral prefrontal-amygdala neural system regional brain morphology and chemical patterns in children with mood disorders compared to a healthy comparison group of children.

*Hypothesis1A*: At both baseline and follow-up, AMYG volumes will be lower in children with mood disorders compared to healthy comparison (HC) children.

*Hypothesis 1B:* Age-related OFC volume reductions will be greater in children with mood disorders than in HC.

Exploratory analyses will also be conducted to explore the possibility of volumetric differences across diagnostic groups and in other brain regions not hypothesized *a priori*.

Aim #2: Use a prospective longitudinal design and fMRI to examine age-related changes in AMYG and

#### APPROVED BY THE YALE UNIVERSITY IRB 6/15/2023

MAY 2023 HIC #0407026910

Principal Investigator: [name]

OFC function in children with mood disorders compared to HC.

*Hypothesis 2A:* At both baseline and follow-up, AMYG activation will be greater in children with mood disorders compared to HC.

*Hypothesis 2B:* Age-related OFC activation increases will be lower in magnitude in children with mood disorders than in HC.

**Aim #3:** Use a prospective longitudinal design and diffusion tensor imaging (DTI) to examine agerelated changes in AMYG and OFC connectivity in children with mood disorders compared to HC.

Exploratory analyses will also be conducted to explore the possibility of functional and connectivity differences across diagnostic groups, and in a small sample at "high-risk" for bipolar disorder, and in other brain regions not hypothesized *a priori* and structure-function relationships.

# **Exploratory Aims:**

**Exploratory Aim #4:** Use structural MRI, in combination with study of allelic variation in genes and associated biochemical factors associated with mood disorders (or behaviors that might contribute to or be related to mood disorders), to examine the potential modifying influence of genetic factors on volume abnormalities in children with mood disorders.

*Hypothesis 4:* The presence of the serotonin transporter (SLC6A4) promoter short ("s") allele will be associated with greater AMYG volume increases in children with mood disorders than in HC.

**Exploratory Aim #5:** Use fMRI, in combination with study of allelic variations in genes and associated biochemical factors associated with mood disorders (or behaviors that might contribute to or be related to mood disorders), to examine the potential modifying influence of genetic factors on functional abnormalities in children with mood disorders.

*Hypothesis 5:* The presence of the serotonin transporter (SLC6A4) promoter short ("s") allele will be associated with greater AMYG activation increases in children with mood disorders than in HC

In addition, we will study effects on MRI measures of allelic variation at other strongly favored candidate loci, including, for example, any specific mood disorder risk loci that may be identified over the course of the study. Exploratory analyses will also be performed for the potential modifying influence on AMYG and OFC structure and function of other demographic and clinical factors such as sex, medication exposure, current medications, presence of rapid-cycling, duration of illness, smoking history, family-loading for mood disorders, stressors and socioeconomic status.

**Exploratory Aim #6**: Use MRI, in combination with the study of allele variation in genes and associated biochemical factors and assessments of stress, to examine the potential interaction between genes and stress in influencing the development of AMYG-OFC circuitry and the emergence of disorders of mood and impulse regulation (ADHD and substance use disorders).

*Hypothesis 6A:* Adolescents with high stress exposure, as compared to adolescents with low stress exposure, will show heightened AMYG and ventral striatum response and diminished OFC response to emotional face stimuli.

*Hypothesis 6B*: Abnormal response in the AMYG-ventral striatum-OFC neural system will be associated with impulsive and addictive behaviors.

*Hypothesis 6C:* Adolescents with high stress exposure who are 5-HTTLPR (SLC6A4) "s" carriers will show both the greatest magnitude of circuitry dysfunction and addictive behaviors.

**Exploratory Aim** #7: Investigate changes in corticolimbic system functioning during emotional regulation and to use fMRI, before, at mid-point, and after an emotional regulation intervention, to assess intervention-associated changes in AMYG and OFC responses to emotional stimuli and functional connectivity and if incorporating actigraphy, investigate objective cross-domain peripheral measures of daily rhythm regularity at high temporal resolution.

*Hypothesis 7A*: The emotional regulation psychotherapy treatment will be associated with "normalization" of the circuitry and symptom improvement.

*Hypothesis 7B*: Integrating actigraphy and EMA will provide objective and high temporal resolution data about how daily rhythm's change with BE-SMART behavioral therapies.

**Exploratory Aim #8:** Use 7T MRI and magnetic resonance spectroscopy (MRS) to investigate amygdala anatomy at high resolution and to study glutamate neurotransmitter levels in the amygdala *Hypothesis 8:* The volume of the lateral nucleus of the amygdala will be decreased, and there will be differences in amygdala glutamate levels, in adolescents with mood disorders.

2. **Background:** Describe the background information that led to the plan for this project. Please provide references to support the expectation of obtaining useful scientific data. When available, previous work in animal and/or human studies should be included.

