## Modifying Influence of Genotypes on Amygdala Function in BD: Pilot Data:

The data above was examined for potential increases in AMYG activity in association with the serotonin transporter promoter protein SLC6A4 "s" allele. We found that BD subjects who are "s" carriers (i.e. "ss" or "ls") have significantly higher left AMYG volume as well as activation (p<0.05) than those with "ll" genotype. This suggests that the "s" allele may influence a shift in neuroprotection towards greater

volume but that volume increases may be associated with some maladaptive functional features such as abnormal emotional processing.

**Note:** While we have focused on the AMYG and OFC in this proposal, other brain structures including medial temporal regions such as the hippocampus and other frontocortical structures have also been implicated in BD. Exploratory analyses will be performed to investigate potential group differences in these and other brain regions identified as potential regions of difference on whole brain structural and functional analyses.

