# **MRI Data Processing:**

Image processing and analysis will be performed at the Yale MR Center on UNIX workstations using standard as well as locally developed software. Data are stripped of all identifying information and assigned a numerical code so that image processors are blind to subject information. Processing will include transformation of brains across subjects into common stereotactic space. Pre-existing subjects who had consented to share their samples and data may have their post processed MRI data along with de-identified information in computer files about their processed samples sent to the University of Iowa as part of a GWAS. Yale is not receiving information from University of Iowa for this study.

- **4. Statistical Considerations:** Describe the statistical analyses that support the study design. This section should include:
  - The number of subjects expected to enter the study.
  - A statement about the statistical power of the study to test the major hypothesis.
  - A summary of the plans for data analysis.

Hypothesis testing will be performed with region of interest measures as the dependent variables, analyzed in mixed models in consultation with a statistician, e.g. with current collaborators such as [name] (EPH) and [name] (GCRC). For example, to test hypothesis #1: diagnosis will be the between subject's variable. Hemisphere (right vs. left) and time (1st scan vs. 2nd scan) will be the within-subject variables and there will be a random subject effect. Repeated measures will be performed over the spatial domain of hemisphere. Total brain volume will be included as a covariate to control for general scaling effects. Terms that are not significant (p>0.05) will be eliminated via a backward stepwise algorithm, with the constraint that the model at each step is hierarchically well-formulated. Least squares means (Is means) and standard errors (SE) will be calculated in the mixed model and plotted to interpret significant interactions.

Whole brain analyses will also be performed to examine for group differences in regions not hypothesized *a priori*. These will be performed with widely available software such as SPM software as well locally developed software.

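### Hypothesis 6C predicts only which genotype-stress group is worst, a pattern that additive effects also produce, so support for it would not establish the interaction Aim 6 asks about

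*Combined protocol and SAP*

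**What the plan says.** Section III, item 1, Exploratory Aim #6 sets out to use MRI with genetic, biochemical and stress data "to examine the potential interaction between genes and stress in influencing the development of AMYG-OFC circuitry" and the emergence of mood and impulse disorders. It has three hypotheses:

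- 6A is a stress contrast: "Adolescents with high stress exposure, as compared to adolescents with low stress exposure" are expected to have higher amygdala and ventral striatum response and lower orbitofrontal (OFC) response to emotional faces.
- 6B is an association between circuit response and impulsive or addictive behaviour.
- 6C brings in genotype: "Adolescents with high stress exposure who are 5-HTTLPR (SLC6A4) 's' carriers" "will show both the greatest magnitude of circuitry dysfunction and addictive behaviors".

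Section III, item 4 (Statistical Considerations) says that hypotheses will be tested in mixed models with region-of-interest measures as outcomes. It writes out one model, as an example: "For example, to test hypothesis #1: diagnosis will be the between subject's variable". The other terms are hemisphere, time, a random subject effect and total brain volume. Two general rules follow. "Terms that are not significant (p>0.05) will be eliminated via a backward stepwise algorithm", subject to the model staying hierarchically well formed, and least squares means "will be calculated in the mixed model and plotted to interpret significant interactions". No genotype, stress or genotype-by-stress term is named for Aim 6.

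The background pilot data report that, within bipolar disorder, s carriers "have significantly higher left AMYG volume as well as activation (p<0.05) than those with 'll' genotype". Stress level does not enter that comparison.

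**The concern.** An interaction means that the effect of stress differs between s carriers and the ll genotype. Hypothesis 6C says something weaker: of the four genotype-by-stress groups, the doubly exposed one is worst. Two separate adverse effects that simply add up give the same picture. The plan itself expects one of them (6A, for stress), and its pilot data suggest the other (for the s allele, on the amygdala, within bipolar disorder).

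A report that 6C was supported could therefore be read as evidence of a gene-by-stress interaction when only two main effects are present. The statistical section does not close the gap, because it names no test of the interaction for this aim. Its elimination rule, if applied here, could remove the one term that would answer the question and still leave a fitted pattern that agrees with 6C.

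**Working it through.** **No plan figure to reproduce.** The documents give no sample size, effect size or power for Aim 6. The only power statement (Section III, item 4, Power) concerns diagnosis differences in amygdala and OFC volume and has no bearing on 6C.

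**Step 1: algebra, which needs no assumed numbers.** Orient each outcome so that higher is worse; for OFC response this means reversing the sign, because 6A defines dysfunction there as a diminished response. Let g be the s-allele effect, s the stress effect and i the interaction. The four expected means are:

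| | low stress | high stress |
|---|---|---|
| ll | 0 | s |
| s carrier | g | g + s + i |

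The doubly exposed group is the largest when

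- g + s + i > g, that is i > -s, and
- g + s + i > s, that is i > -g.

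With g and s both positive, the comparison with the zero cell then follows. The condition is i > -min(g, s). It holds at i = 0, and also for a moderately negative interaction. For example, with g = s = 0.5 and i = -0.3 the means are 0, 0.5, 0.5 and 0.7.

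**Step 2: what elimination would do.** If a genotype-by-stress term were entered and had p>0.05, the rule would drop it. An additive model with two positive coefficients always has its highest fitted mean in the doubly exposed group, so 6C would still look supported.

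**Step 3: simulation, for illustration only.** Assumed inputs: N=100 (the size of the adolescent cohort in Section II, item 5; its link to Aim 6 is an assumption), half with high stress, 50-70% s carriers, SD 1, correlation 0.3 between the two outcomes, 40,000 replicates. Two readings of support are compared:

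| s-allele effect, stress effect, interaction (SD) | Highest mean on both outcomes | Exceeds each other group at p<0.05 on both outcomes |
|---|---|---|
| 0.3, 0.3, 0 | about 60-62% | about 1% |
| 0.4, 0.4, 0 | about 76-78% | about 4% |
| 0.5, 0.5, 0 | about 87-89% | about 9-10% |
| 0, 0.4, 0 | about 26-28% | about 0.1% |
| 0, 0, 0 | about 7-9% | about 0% |
| 0.5, 0.5, -0.3 | about 43-45% | under 1% |

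**Step 4: the direct test.** The interaction contrast is m(s carrier, high) - m(ll, high) - m(s carrier, low) + m(ll, low). On a single outcome with 25 per group:

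- Under additivity it rejects in about 5% of replicates, as it should.
- Its standard error is sqrt(4 × 1/25) = 0.40 SD, so the 95% interval is about ± 1.985 × 0.40 = ± 0.79 SD.
- Power for a true interaction of 0.5 SD is about 23%, and about 22% with 65% carriers. A p>0.05 rule would then discard a real interaction of that size in roughly 77-78% of studies.

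**The case against.** The strongest reply is that 6C is a directional expectation and not a decision rule. The plan nowhere says that 6C is met when one raw mean comes out on top. Item 4 calls for mixed models, gives hypothesis #1 only as an example, and uses least squares means to interpret interactions that are significant. An analyst working in that framework could well fit genotype by stress.

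Much of this stands. A reader might infer that the study would declare an interaction in 60-89% of cases when none exists. The documents do not support that, because those rates belong to a ranking with no inference. Requiring significance against each other group brings them down to about 1-10%. That stricter reading is also a construction, since the plan specifies neither. A reader might also infer that Aim 6 cannot be answered. That goes too far as well: the aim itself names the interaction, and the wording of 6C does not prevent its being analysed.

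What the reply does not remove is the mismatch. Even the stricter reading is a set of pairwise comparisons that additive effects truly satisfy, so its rate rises with sample size and effect size without any interaction. The framework's capacity to hold the term is not a commitment to fit it, keep it or base the claim on it.

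The exploratory label and the low power of the direct test are both fair points. They lower the priority, and they argue for an estimate with an interval. They do not make a pattern that additivity also produces into evidence of interaction.

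**Conclusion.** The point holds as a mismatch between an aim and its hypothesis. Support for 6C as worded would not by itself establish a gene-by-stress interaction, because adverse additive effects give the same pattern, as does any interaction above -min(g, s). This rests on the wording and the algebra alone. Its one condition is that both main effects are adverse. Hypothesis 6A predicts this for stress. For the s allele the only support is pilot amygdala data within bipolar disorder, and carrying that over to the adolescents of Aim 6, or to addictive behaviours, is an assumption.

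The simulated percentages are illustrations. The documents give no sample size for Aim 6, stress cut-off, carrier share, effect sizes or outcome correlation. Severity is low: the aim is exploratory, and no primary aim or sample size depends on it.

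**What to change.** Restate 6C as a genotype-by-stress interaction in a model that contains both main effects, and fix the direction for each outcome:

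- amygdala and ventral striatum response, and addictive behaviours: stress effect more positive in s carriers than in ll;
- OFC response: stress effect more negative in s carriers than in ll.

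A single requirement of a positive coefficient would be wrong, since for OFC it would count a result against the hypothesis as support. State the scale on which each outcome is analysed, because additivity depends on it.

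In Statistical Considerations, add a line naming this model for Aim 6 and exempting the interaction from backward elimination. Report its estimate with a 95% confidence interval whatever the p-value, show the four group means as description, and claim a gene-by-stress interaction only from that term.

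The cost is a reworded hypothesis and a model line, with no new data or procedures. The downside is a wide interval (about ± 0.8 SD at the assumed N=100), so the claim will often be less favourable than a statement about the worst group.
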